6.6 Mutational Analysis

Note: As of Protocol Version 7/ Amendment 6, samples for mutational analysis are no longer being collected.

Bone marrow aspirate and peripheral blood samples for exploratory assessments of cancer-associated mutations and/or genetic alterations will be collected as follows:

A bone marrow aspirate sample will be collected during the Screening period, prior to Cycle 1 Day 1. If the patient had a bone marrow aspirate performed within 28 days of Cycle 1 Day 1 and there is sufficient sample available for analysis, it does not need to be repeated.

At any time while on treatment, if a patient undergoes a bone marrow aspirate or biopsy sample collection for response assessment, material will be requested for cancer-associated mutations analysis (refer to Section 4.3 and Section 6.3 for timepoint details).

Peripheral blood samples will be collected at Screening and at each timepoint that a bone marrow aspirate or biopsy is obtained.

See the laboratory manual provided for details of the specific analyses and instructions on collecting and processing of these samples.

^a Collected in dose-expansion patients during C2D2 and at the end of 72 hr FT-2102 washout (C2D4) (see Schedule of Events in Appendix 1).

b Not required in Phase 2.

Note: Pretreatment bone marrow aspirate and peripheral blood samples for retrospective confirmation of IDH1m by the central assay is mandatory for efficacy evaluable (EE) population definition, and not an exploratory assessment.

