The exploratory objectives are:

Phase 1 and Phase 2

- To assess on-target activity of FT-2102, as determined by changes in a PD biomarker in plasma
- To determine the frequency of cancer-associated mutations and/or genetic alterations in responding and nonresponding patients
- To evaluate PK/PD and clinical response relationships in each cohort

Phase 2

• To evaluate the health-related quality of life (QOL) of patients receiving FT-2102 as a single agent or in combination with azacitidine

III. Study Endpoints

A. Primary

The primary endpoints are:

Phase 1

• Incidence and severity of adverse events (AEs), clinical laboratory abnormalities, and changes in electrocardiogram (ECG) parameters

Phase 2

- All cohorts except Cohort 2: Complete Response rate (best overall response [BOR] of complete remission (CR)/complete remission with partial hematological recovery (CRh)) as determined by the investigator per disease-specific criteria. Refer to Appendix 6 for AML and Appendix 7 for MDS response criteria in the protocol.
- Cohort 2: Four-month relapse free survival (RFS) rate

B. Secondary

The secondary endpoints are:

Phase 1

- PK parameters derived from FT-2102 concentrations
- Antileukemic or antimyelodysplastic activity as determined by CR, CRh, complete remission with incomplete blood count recovery (CRi), morphologic leukemia-free state (MLFS), Marrow CR, partial remission (PR) and stable disease (SD)

Phase 2

- Evidence of clinical benefit (CRi, MLFS, Marrow CR, Overall Response (OR), Transfusion Independence (TI), Time to Response (TTR), Duration of Response (DOR), event free survival [EFS], RFS, Overall Survival (OS), and other definitions of response, including SD)
- Incidence and severity of adverse events (AEs), clinical laboratory abnormalities and changes in electrocardiogram (ECG) parameters
- PK parameters derived from plasma FT-2102 concentrations

IV. Study Design

A. Design Overview

This Phase 1/2 study will utilize a multicenter, open-label, dose-escalation design, to evaluate the safety, efficacy, PK, and PD of FT-2102 administered orally to patients with AML or MDS. Patients will be given FT-2102 daily (QD or BID) in continuous 28-day cycles, alone or in combination with azacitidine (administered at the dose of 75 mg/m² for 7 days IV/SQ per every 28-day cycle) or low-dose cytarabine (LDAC) (administered at the dose of 20 mg BID SC for 10 days every 28-day cycle) until treatment discontinuation.

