Unless stated otherwise, missing data will not be imputed. However, if there are dates missing for AEs or medications, some intermediate steps may be taken for the determination of being treatment emergent or not. Sections below address such procedures for the handling of those dates in the relevant analyses:

Missing or Partial AE or Medication start or stop date:

For missing or partial start-dates:

- 1. If the onset date is unknown, then the date will not be imputed and will be assigned a missing value.
- 2. If the month and day are unknown, then:
 - a. If the year matches the year of the first dose date, then impute the month and day of the first dose date.
 - b. Otherwise, assign as missing.
- 3. If the day of the month is unknown, then:
 - a. If the month and year match the month and year of the first dose date, then impute the day of the first dose date.
 - b. Otherwise, assign as missing.

For partial end-dates:

- 1. If the year is unknown, then the date will not be imputed and will be assigned a missing value.
- 2. If the month is unknown, then assign as missing.
- 3. If the day is unknown, then assign the last day of the month.

Missing Pharmacokinetic (PK) Data:

Missing FT-2102 concentration data in a given profile will not be imputed. Missing samples will be reported as no sample ("NS") and excluded from analysis. The affected

profile(s) will be evaluated whether sufficient FT-2102 concentrations are available to calculate any of the planned PK parameters.

FT-2102 concentrations below the lower limit of quantitation (LLOQ) will be indicated by BLQ in the listings and will be treated as follows:

• For predose samples prior to the FT-2102 administration: Concentrations that are BLQ or missing will be assigned a numerical value of zero for the calculation of AUC. Any anomalous concentration values observed at predose will be included in the computation of AUC. If the predose concentration is greater than 5% of C_{max}, the data will be evaluated on a case-by-case basis to determine if exclusion of the affected profile is warranted.

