Subgroup Name	Levels	Additional Details, if applicable		
		(140 - age) * baseline weight (kg) * (0.85 if		
		female) /		
		(72 * baseline serum creatinine [mg/dL])		

K. Data Display Characteristics

Data displays produced for this study will include three types—summary tables, data listings, and figures. Unless stated otherwise, data listings will be produced for all recorded data as well as derived variables. Summary tables will be produced as specified in following sections. Figures will be produced when specified in sections to follow.

Listings will be ordered by phase, treatment (dose and schedule), cohort, patient number, and nominal visit. When expedient, additional levels of ordering hierarchy may reflect subsets of assessments within patient. Data listings will not display patient initials.

Tables will be organized differently based on the purpose of the data analysis being performed: interim safety analyses or formal interim analysis or final analysis. Data snapshots taken for the purpose of safety analysis (regulatory reporting, IB update, etc.) will be organized as outlined in Appendix 3. Table generation for interim futility and efficacy analyses as well as final analyses will be organized as specified in Appendix 3.

The summary statistics displayed will be a function of the type of data associated with the summarized assessment. Unless stated otherwise in relevant sections to follow, continuous data will be summarized with the number of non-missing values, mean, standard deviation, minimum, median, and maximum. Categorical data will be summarized with the number of non-missing values and the numbers of values equal to each of the possible values. Percentages of patients with each of the possible values will be calculated from the number of patients in the corresponding analysis set, unless stated otherwise. Some continuous variables may also be grouped into categorical levels and evaluated in frequency tables.

L. Blinded Review of Data

Not applicable for this study, as it is open label.

VII. Baseline Patient Characteristics and Disposition

A. Disposition

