- Refractory relapse: patients that enter the study who have relapsed to a prior line of therapy and then became refractory to an attempt of salvage therapy.

Disease history will be summarized separately for AML and MDS patients. The denominator for percentages will be the number of patients with that disease (AML or MDS).

Time from diagnosis in months will be calculated by subtracting the diagnosis date from the informed consent date, and dividing the number of days by 30.4375, and rounding to one decimal place.

The total number of prior regimens received (based on the prior therapies CRF) will be summarized both by descriptive statistics (mean, standard deviation, median, minimum, maximum) and categorically (number of regimens received: 1, 2, 3, or 4 or more). The site enters regimen number into the CRF (i.e., a single regimen may be comprised of one or more drugs). The maximum regimen number for each patient will be used for tabular summarization of total number of prior regimens.

The number of patients who have received various types of treatment regimens (induction, re-induction, consolidation, salvage, maintenance, autologous HSCT, allogenic HSCT, transplant-DLI, and conditioning) will be tabulated. This information is taken from the prior therapies CRF.

D. Cytogenetics and Molecular Genetics

The following information collected about genetic mutations will be summarized for the FAS (both phases) and for the EE analysis set. The cytogenetics summary will also be produced by subgroup for the following subgroups: disease state (relapsed/refractory vs. treatment naive) for Phase 1 patients only.

Data will be listed for all patients in the FAS. The following data will be summarized separately for AML and MDS patients. The denominator for percentages of patients having a certain mutation will be the number of patients with that disease (AML or MDS).

- Cytogenetic risk classification per CRF
- Cytogenetics per CRF
- Result of central test of IDH1 mutation
- IDH1 mutation type at baseline per CRF
- IDH1 mutation type at baseline per companion diagnostic
- Total number of co-mutations at baseline per CRF
- Incidence of co-mutations at baseline per CRF

E. Baseline Disease Characteristics

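### SAP VII.D divides each baseline mutation percentage by all AML or MDS patients, so any gap in gene testing lowers the reported frequency

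*SAP*

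**What the plan says.** SAP VII.D (Cytogenetics and Molecular Genetics) sets the scope of the table: "The following information collected about genetic mutations will be summarized for the FAS (both phases) and for the EE analysis set". Among its rows are the total number of co-mutations and "Incidence of co-mutations at baseline per CRF". AML and MDS are shown separately, and the divisor is stated outright: "The denominator for percentages of patients having a certain mutation will be the number of patients with that disease (AML or MDS". The section does not mention patients in whom a gene was not tested.

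Three other rules bear on this:

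- SAP VI.K (Data Display Characteristics) asks for a non-missing count: "Categorical data will be summarized with the number of non-missing values and the numbers of values equal to each of the possible values".
- The same section sets the default divisor: "Percentages of patients with each of the possible values will be calculated from the number of patients in the corresponding analysis set, unless stated otherwise". That default is not restricted to tested patients either.
- SAP VI.C (Missing Data/Data Imputation) adds: "Unless stated otherwise, missing data will not be imputed".

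On what must be tested, Protocol 4.4.1 (criterion 2) requires only a site-documented IDH1-R132 mutation. No section requires the sites to run the same co-mutation panel.

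**The concern.** A co-mutation can be recorded only in a patient whose gene was examined. When the divisor is everyone with the disease, a patient with no result adds one to the denominator and can never add to the numerator. In the percentage, that patient has the same effect as a negative result. The error can go only one way, and it may differ from gene to gene and from cohort to cohort, depending on what each site tests.

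What is at stake is how the molecular profile of the enrolled population is read, including any comparison with another population in which frequencies were calculated among tested patients.

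The plan treats a similar gap differently elsewhere. In the subgroup table of SAP VI.J, patients whose cytogenetic risk is not known are left out of the cytogenetic-risk subgroups.

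**Working it through.** The plan states no figure to reproduce. The check is how the stated divisor behaves when testing is incomplete.

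**Inputs**
- Divisor: all patients with the disease (SAP VII.D).
- N = 190, used for illustration: the approximate planned enrolment of Phase 2 Cohort 1, an all-AML cohort (SAP IV.C).
- Frequency among tested patients, p = 20%: assumed.
- Share tested, c: assumed over a range, because the documents do not give it.

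**Formula**
- Number tested t = c × N. Number with the mutation recorded m = p × t.
- VII.D percentage = m / N = p × c.
- Percentage among tested = m / t = p.
- The ratio of the first to the second is c, so the relative shortfall equals the untested share.

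**Direct results for p = 20%**
- c = 100%: 0.20 × 1.0 = 20%
- c = 90%: 0.20 × 0.9 = 18%
- c = 80%: 0.20 × 0.8 = 16%
- c = 60%: 0.20 × 0.6 = 12%

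**Whole patients, N = 190**

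| Assumed coverage | Tested | With mutation | VII.D percentage | Percentage among tested |
|---|---|---|---|---|
| 100% | 190 | 38 | 20.0% | 20.0% |
| 90% | 171 | 34 | 17.9% | 19.9% |
| 80% | 152 | 30 | 15.8% | 19.7% |
| 50% | 95 | 19 | 10.0% | 20.0% |

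The last column moves only through rounding to whole patients. The proportional effect is the same for other frequencies. At 80% coverage, an assumed 10% is shown as 15/190 = 7.9%, and an assumed 30% as 46/190 = 24.2%.

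**Selective testing**

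Reading p as the frequency in the whole cohort assumes that testing is unrelated to mutation status. Without that assumption the data only bound the frequency. At 80% coverage, 190 − 152 = 38 patients are untested:
- If none of them carries the mutation, the cohort frequency is 30/190 = 15.8%.
- If all of them do, it is (30 + 38)/190 = 68/190 = 35.8%.

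The VII.D percentage is therefore the lower bound. The percentage among tested patients (19.7%) lies inside the range, and would be too high if sites tested mainly patients in whom they expected the mutation.

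**The case against.** The best defence is that this is a baseline listing with a conventional denominator. SAP VII.C uses the same rule for disease history, VI.K asks for non-missing counts, and VII.D lists the data for every FAS patient. Nothing is imputed, and the SAP nowhere recodes an untested patient as negative. A reader given the number tested for each gene could rebuild the percentage. Much of this stands. It falls short because VI.K does not say that the count will be shown per gene, and the SAP does not define a non-missing co-mutation result. The unadjusted percentage would remain the printed figure.

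Four stronger readings are tempting, and the documents do not carry them.

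- *Frequencies will be understated.* This depends on incomplete testing. Coverage is not given, and the CRF and laboratory manual are not available here. With full testing there is no shortfall.
- *The comparison of responders with non-responders is biased.* The SAP does list an exploratory objective on this: "To determine the frequency of cancer-associated mutations and/or genetic alterations in responding and nonresponding patients". But VII.D contains no split by response. Protocol 9.2.7, which plans the correlation with response, states no denominator, and the protocol synopsis assigns the mutation assessment to a central laboratory rather than the CRF. Nothing extends the VII.D rule to that analysis.
- *Amendment 6 shows that data are missing.* Protocol 6.6 says that "samples for mutational analysis are no longer being collected", but this concerns study samples for exploratory work. It does not say that sites stop entering co-mutation results on the CRF, which is the source VII.D uses.
- *The total co-mutation count has the same fault.* The denominator sentence governs percentages for a given mutation and does not clearly reach a count. What is missing there is a rule on whether an untested patient's count is zero or missing.

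The caution about selective testing also stands: simply replacing one divisor with the other could overstate frequency.

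**Conclusion.** The point holds in a limited form. VII.D states an all-patient divisor for mutation percentages, and nothing in the entry criteria guarantees a result for each co-mutation gene in each patient. If results are missing, the relative shortfall equals the untested share: 10%, 20% or 40% at coverage of 90%, 80% or 60%. Whether there is a shortfall, and how large, cannot be known from the documents.

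The effect is confined to descriptive baseline genetics tables. The CR/CRh test, sample size, alpha and stopping rules are untouched, and co-mutations are not among the subgroups named in SAP VI.J. Site-reported IDH1 results are little affected, because a site result is needed for entry. A reader might infer that the trial's response-by-mutation findings are compromised; the documents do not support that. This is a reporting weakness that should be corrected because correcting it costs very little.

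**What to change.** In SAP VII.D:

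- For each gene, show the number tested and the number not tested or unknown.
- Calculate the percentage among patients with a recorded positive or negative result. The all-patient percentage may be kept beside it, labelled as such.
- Add a footnote that testing may have been selective. Where the CRF does not separate negative from not tested, say so.
- Treat an untested patient's total co-mutation count as missing, not zero.
- If mutation frequencies are reported by response under Protocol 9.2.7, use the same tested-patient denominator and show the number tested in each response group.

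The cost is a few lines of SAP text, a tested flag in the analysis dataset where the CRF allows it, and smaller denominators for some genes. No new patient data are needed.

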7.3 Classification of Adverse Events by Severity

The severity refers to the intensity of the AE. The Investigator must categorize the severity of each AE according to the NCI CTCAE version 4.03 (see Appendix 4). CTCAE guidelines can be referenced at the following website: http://ctep.cancer.gov/reporting/ctc.html.

For any term that is not specifically listed in the CTCAE scale, intensity will be assigned a grade of one through five using the following CTCAE guidelines:

Grade 1: Mild; asymptomatic or mild symptoms, clinical or diagnostic observations only; intervention not indicated

Grade 2: Moderate; minimal, local or noninvasive intervention indicated; limiting age-appropriate instrumental activities of daily living

Grade 3: Severe or medically significant but not immediately life-threatening; hospitalization or prolongation of hospitalization indicated; disabling; limiting self-care activities of daily living

Grade 4: Life-threatening consequences; urgent intervention indicated

Grade 5: Death related to AE

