9.2.4.2 Safety Analysis

For DLT-evaluable patients, the summary of DLTs will be provided by dose/dosing schedule for patients in the Phase 1 dose-escalation stage. All other safety analyses will be based on the Safety Set.

For each stage, the safety and tolerability of FT-2102 will be assessed, as evaluated by adverse events, concomitant medication usage, changes from baseline in physical examination, vital signs, clinical laboratory evaluations, and ECG. Safety data will be listed by patient and summarized descriptively.

A treatment-emergent adverse event (TEAE) is defined as an adverse event with onset on or after the start of study drug, or any worsening of a pre-existing medical condition/adverse event with onset on or after the start of study drug and until 28 days after the last dose. For each stage, all adverse events will be coded using MedDRA version 19.1 or higher and summarized by SOC and PT, for each treatment group. Multiple occurrences of an AE are counted only once per patient per SOC and PT for summary tables. Causality of TEAEs (not related, related) and severity (NCI CTCAE version 4.03 or higher) will be summarized by treatment for each stage.

Relationship will be presented by study drug when applicable. All adverse events and serious adverse events (including those with onset or worsening before the start of study drug) will be listed.

Safety laboratory, vital sign, ECG and physical examinations will be summarized by visit. The change from baseline will be presented along with the by-visit summaries. Shifts in laboratory grades, as well as QTcF shifts, will be tabulated. Assessment of changes in liver function tests will be conducted. Abnormal safety assessments will be flagged and separately presented. All safety data will be listed.

Assessment of differentiation syndrome will be conducted as per Montesinos et al. 2009, searching for candidate cases of differentiation syndrome based on AE reports of dyspnea, pulmonary infiltrates, edema, weight gain, pleural effusion, renal failure, hypotension, pericardial effusion, and unexplained fever. Specific methods of identifying candidate cases will be fully described in the Statistical Analysis Plan (SAP).

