Adverse Events (AEs) will be summarized and recorded from the time of first dose through 28 days after the last dose of study drug, and serious adverse events from the time of informed consent to 28 days after the last dose of study drug. AEs will be coded using the MedDRA dictionary version 19.1, with verbatim terms coded by System Organ Class (SOC) and Preferred Term (PT) and graded via the CTCAE version 4.03. Sponsor coding conventions will be applied during the creation of analysis datasets. Therefore, the raw dataset may reflect a different preferred term than the ADAE data set.

A treatment-emergent AE (TEAE) is an AE that emerges after the first dose of study drug through 28 days post last dose, having been absent pretreatment, that occurred on or after the first dose of study treatment or within 28 days after the last dose, or occurred prior to the first dose and increased in grade during study treatment. If an AE has partial onset date, the imputed onset date as specified in Section VI.C will be used to define TEAE.

The causality of an AE includes related or unrelated. A treatment-related AE is defined as an AE considered "Possibly Related", "Probably Related", or "Definitely Related" to the study drug by the investigator. Missing relationship will be treated as unknown and excluded from summary of treatment-related AEs considered to be related; events reported as "Definitely Not Related", "Probably Not Related", or "Unlikely" will be considered not related.

If the AE start or stop date is still missing after implementing the rules specified in Section VI.C, the following strategy will be used to determine whether AEs with missing start or stop dates are pre-treatment or treatment-emergent:

- 1. If the start date and stop date are both missing, the most conservative approach is taken, and the AE is considered to be treatment-emergent.
- 2. If the start date is missing but the stop date is not missing and is after the day of study dose administration, then the most conservative approach is taken, and the AE is considered to be treatment-emergent.
- 3. If the start date is missing but the stop date is not missing and is on or before the day of study dose and after the date of signed informed consent, then the AE is considered to be pre-treatment (not TEAE).

The following AE summaries will be produced for both Phase 1 and 2:

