- Overall Summary of AEs. This will include the total number of AEs, the total number of TEAEs, the total number of treatment-related TEAEs, and the number of patients with: at least one TEAE, at least one treatment-related TEAE, at least one Grade 3 or higher TEAE, at least one Grade 4 or higher TEAE, at least one treatment-related Grade 4 or higher TEAE, at least one treatment-related Grade 4 or higher TEAE, at least one treatment-related Grade 4 or higher TEAE, at least one treatment-related Grade 4 or higher TEAE, at least one treatment emergent serious adverse event (TESAE), at least one related TESAE, at least one TEAE that led to study drug discontinuation, at least one TEAE that led to dose modification, and TEAE leading to death.
- Summary of TEAEs by system organ class and preferred term, or by preferred term. For each event term, the numbers and percentages of patients experiencing an AE with that term will be summarized. If a patient reports the occurrence of a particular adverse event more than once, the event is only counted once.
- Summary of TEAEs by system organ class, preferred term, and grade: if a patient has multiple AEs the most severe/ related one will be utilized for the summary. This summary will be presented for a limited subset of patients total Phase 1 single agent FT-2102 patients; total Phase 1 combination therapy patients; total Phase 2 single agent Cohort 1 patients; total Phase 2 single agent patients overall; and total Phase 2 combination therapy patients. A similar summary of TEAEs will be produced by preferred term and grade.

Summaries by system organ class and preferred term will be sorted alphabetically by system organ class, and alphabetically by preferred term within system organ class. Summaries by preferred term will be sorted in descending frequency per the Overall column for the table.

TEAE Set	By SOC and PT	By SOC, PT, and Grade	Ву РТ	By PT and Grade
TEAEs	Х	Х	Х	Х
Treatment-related TEAEs	Х		Х	
TEAEs of G3 or G4	Х		Х	
Treatment-related TEAEs of G3				
or G4	Х		Х	

The table below indicates the types of summaries that will be provided for various sets of TEAEs:

TEAE Set	By SOC and PT	By SOC, PT, and Grade	By PT	By PT and Grade
TESAEs	Х			
Treatment-related TESAEs	Х			
TEAEs leading to withdrawal from study drug	х			
Treatment-related TEAEs leading to withdrawal from study drug	х			
TEAEs leading to dose modification	Х			
Treatment-related TEAEs leading to dose modification	Х			
TEAEs leading to death	Х			

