Treatment-related TEAEs leading to death	Х			
TEAE of Special Interest	X			

All AEs occurring on study (treatment emergent or not) will be provided in patient data listings. The following additional by-patient listings of AEs (treatment emergent or not) will be provided: all SAEs, all AEs leading to withdrawal of study drug, all AEs leading to dose modification, and all AEs leading to death.

In addition, a listing of all deaths with related information regarding the death will be provided, including AEs leading to death, as well as deaths that are not reported as due to an adverse event.

A summary of DLTs by system organ class and preferred term, and a listing of all AEs that caused a DLT, will be provided for the DLT evaluable set.

Adverse Events of Special Interest (AESI): Hepatotoxic and Gallbladder disorder

Some patients taking FT-2102 have experienced transaminase elevations. As such, summary tables of AEs for hepatotoxicand gallbladder disorders will be created, with tabulations of the number of patients experiencing such events by SOC and PT. Under each PT within each grouping, the time to onset will be summarized descriptively, and time to resolution will be summarized using Kaplan-Meier (KM) methods.

In addition, overall summary table for TEAEs for each AESI group will be created. It will include the number of patients with TEAEs, treatment-related TEAEs, grade 3 or 4 TEAEs, treatment related grade 3 or 4 TEAEs, serious TEAEs, treatment related serious, TEAEs resulting in FT-2102 discontinuation, treatment related TEAEs resulting in FT-2102 discontinuation; TEAEs leading to dose reduction, TEAEs leading to dose hold, treatment related TEAEs resulting in on-treatment death, treatment related TEAEs resulting in death.

All TEAEs in each group occurring on study will be provided in corresponding patient data listings.

The table below presents preferred terms in each subgroup:

Hepatotoxicity Grouping	Gallbladder disorder Grouping
Alanine aminotransferase increased	Biliary tract disorder
Aspartate aminotransferase increased	Biliary colic
Hypertransaminasemia	
Liver function test abnormal	Cholangitis
Liver function test increased	Cholestasis
Transaminases increased	
Blood alkaline phosphatase increased	
Hyperbilirubinemia	
Blood bilirubin increased	

AESI: Differentiation Syndrome

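### Adverse events with missing causality drop out of every treatment-related summary, and the Grade 3/4 term tables and hepatic/gallbladder summary stop short of Grade 5

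*SAP*

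**What the plan says.** **Causality.** SAP VIII.B has one definition for all related summaries. It begins "A treatment-related AE is defined as an AE considered" and covers events the investigator rated possibly, probably or definitely related. On missing assessments it says: "Missing relationship will be treated as unknown and excluded from summary of treatment-related AEs considered to be related". Protocol 9.2.4.2 plans two categories and has no rule for missing values: "Causality of TEAEs (not related, related) and severity (NCI CTCAE version 4.03 or higher) will be summarized by treatment for each stage".

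**Missing dates.** If start and stop dates are both still missing after imputation, or the start is missing and the stop falls after dosing, the same SAP section says "the most conservative approach is taken, and the AE is considered to be treatment-emergent".

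**Grade.** Protocol 7.3 defines the top grade: "Grade 5: Death related to AE". In SAP VIII.B the overall summary counts patients with "at least one Grade 3 or higher TEAE". The severe-event tables by system organ class and preferred term, and by preferred term alone, cover "TEAEs of G3 or G4", with a related version under the same limit. The summary for hepatotoxic and gallbladder events of special interest counts "grade 3 or 4 TEAEs, treatment related grade 3 or 4 TEAEs". As written, its two death rows (on-treatment death and death) are both limited to treatment-related events.

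**The concern.** A missing causality assessment is handled in the direction that favours the drug, while a missing date in the same section is handled against it. SAP VIII.G also takes the cautious side for missing medication stop dates. Causality is the exception, and no reason is given. The SAP asks for no count of missing assessments, no row for unknown relationship and no sensitivity analysis that treats them as related, so a reader of the related tables could not tell how much was left out.

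The Grade 4 ceiling matters most in the hepatic/gallbladder summary. Protocol 5.5.3 names liver injury as an event of special interest, with potentially associated events in about 20% of patients so far. That summary is where a reader would look for the worst hepatic outcomes, and as specified it can omit a death from the rows meant to show severity and fatality.

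**Working it through.** The plan states no figure here that could be reproduced. The check sets the rules side by side and follows one event through them.

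**1. Reach of the causality rule.** The single definition feeds the related versions of: all TEAEs, Grade 3 or 4 TEAEs, serious TEAEs, withdrawals, dose modifications and deaths, plus the related rows of the hepatic/gallbladder summary. An event with missing relationship leaves all of these. It stays in every all-cause table and in the listings.

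**2. Direction and size.** Let p be the true related rate and m the share of related events with no causality recorded. With one such event per patient, the table shows p × (1 − m). The documents give neither value. Assuming p = 30%:

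| m (assumed) | Calculation | Related rate shown |
|---|---|---|
| 0% | 30 × 1.00 | 30.0% |
| 2% | 30 × 0.98 | 29.4% |
| 5% | 30 × 0.95 | 28.5% |
| 10% | 30 × 0.90 | 27.0% |

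The shift is never upward. In patient counts it is smaller if the patient has another event of the same term that was rated related.

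**3. Where Grade 5 is and is not counted.** A Grade 3/4 row falls short of a Grade 3 or higher row by the patients whose only Grade 3 or higher event of that term is fatal. The overall summary has no such shortfall. The tables by term and grade have no ceiling, but they cover all-cause events only, and only Phase 1 single agent, Phase 1 combination, Phase 2 Cohort 1, Phase 2 single agent overall and Phase 2 combination overall. Fatal TEAEs have their own tables by term, all-cause and related. For differentiation syndrome, the severe category covers Grades 3 to 5 where the investigator reported the event.

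**4. Where the two rules meet.** Take a patient whose only hepatic event of special interest is fatal and has no causality recorded:

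| Output in SAP VIII.B | Counted? |
|---|---|
| Hepatic summary: any TEAE | Yes |
| Hepatic summary: serious TEAE | Yes (death makes it serious, Protocol 7.1) |
| Hepatic summary: discontinuation, dose reduction, dose hold (all-cause) | Only if that action was recorded |
| Hepatic summary: Grade 3 or 4 | No (Grade 5) |
| Hepatic summary: every related row | No (causality missing) |
| Hepatic summary: both death rows | No (related events only) |
| Overall summary: Grade 3 or higher, TEAE leading to death | Yes |
| All-cause tables by term and grade | Yes, in the groups listed in step 3 |
| TEAEs leading to death, all-cause | Yes |
| TEAEs leading to death, related | No |
| Listings | Yes |

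Within the hepatic summary, that death appears only as a TEAE and as a serious TEAE.

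**The case against.** The best defence is that little or nothing will be missing. Protocol 7.4 has the investigator assess the relationship of every adverse event, and Protocol 7.2.3 requires a causality statement in every serious adverse event report. A fatal event with no causality would breach both. This stands as a reason to expect a small effect. It does not remove the point, because the SAP provides for missing relationship and resolves it in one direction.

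The second defence is that reporting Grade 3/4 events and fatal events in separate, clearly labelled tables is an ordinary layout, and that the related-death table by term serves in effect as the related Grade 5 table. This stands for the main tables. It does not cover the hepatic/gallbladder summary, which has no all-cause death row.

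A reader might infer that the plan leaves Grade 5 out of severe-toxicity reporting, or that overall severe toxicity is understated. The documents do not support that: the overall summary, the all-cause by-grade tables, both death tables, the listings and the differentiation syndrome rule all include it. A reader might also infer that the Phase 1 primary endpoint is biased by the causality rule. That endpoint (Protocol 3, SAP III.A) is the incidence and severity of adverse events whatever their cause, and the all-cause tables keep these events.

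Counting missing as related can also overcount, since some of those events will be unrelated. That is fair, and it is why the number missing should be reported alongside.

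**Conclusion.** The concern holds as a minor reporting bias. Treatment-related toxicity can be understated whenever causality is missing, and cannot be overstated by this rule. To say that it *is* understated would go too far, because nothing in the documents shows that any assessment is missing. The Grade 4 ceiling affects only the Grade 3/4 term tables and the hepatic/gallbladder summary. The one real gap is a fatal hepatic or gallbladder event with missing causality, which would miss that summary's severe, related and death rows.

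No event count can be attached. The percentages above rest wholly on assumed rates. Cohort 1's 173 would be the wrong base for scaling them: it is the efficacy-evaluable target, while the Safety Analysis Set is everyone who received any study drug.

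Efficacy is untouched. Dose decisions are too: the dose-limiting toxicity definition (Protocol 4.1.3) includes non-hematological events of Grade 3 and above, and does not use the SAP's treatment-related classification.

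**What to change.** In SAP VIII.B:

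- Count a TEAE with missing relationship as treatment-related in all related summaries. Report how many were missing and flag them in the listing, so that a reader can see how far the related counts depend on the rule.
- Change the Grade 3 or 4 limit to *Grade 3 or higher* in the TEAE term tables, their related versions and the hepatic/gallbladder summary.
- Add an all-cause death row to the hepatic/gallbladder summary.

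The cost is a few wording changes and one extra row. Related and severe counts may be slightly higher. If no causality is missing, the first change alters no number.
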